7.2. Data Listings to be Generated

Listings

Number	Title
Listing 16.2.1.1	Subject Disposition – All Subjects Screened
Listing 16.2.2.1	Major Protocol Deviations – All Subjects Randomized
Listing 16.2.3.1	Subjects Excluded from the Efficacy Analysis – All Subject Randomized
Listing 16.2.4.1	Demographic and Baseline Characteristics - FAS
Listing 16.2.4.2	Ocular Medical History - FAS
Listing 16.2.4.3	Non-Ocular Medical History - FAS
Listing 16.2.4.4	Ocular Surgery History - FAS
Listing 16.2.4.5	Non-Ocular Surgery History - FAS
Listing 16.2.5.1	Treatment Exposure - SAF
Listing 16.2.5.2	Dispense Investigational Product - SAF
Listing 16.2.6.1	Corneal Fluorescein Staining (CFS) Assessment - FAS
Listing 16.2.6.2	Ocular VAS Score - FAS
Listing 16.2.6.3	SANDE Assessment - FAS
Listing 16.2.6.4	Schirmer's Test without Anesthesia Result- FAS
Listing 16.2.7.1	All Adverse Events - SAF
Listing 16.2.7.2	Serious Adverse Events - SAF
Listing 16.2.7.3	Adverse Events leading to Discontinuation of Treatment - SAF
Listing 16.2.7.4	Subject Deaths - SAF
Listing 16.2.8.1	Urine Pregnancy Test - SAF
Listing 16.2.9.1	Slit-lamp Biomicroscopy and External Eye Exam - SAF
Listing 16.2.9.2	Conjunctival Hyperemia Score - SAF
Listing 16.2.9.3	Intraocular Pressure (IOP) Measurement - SAF
Listing 16.2.9.4	Dilated Ophthalmoscopy - SAF
Listing 16.2.9.5	Best Corrected Visual Acuity (BCVA) - SAF
Listing 16.2.9.6	Drop Comfort/Tolerability Assessment - SAF
Listing 16.2.9.7	Prior and Concomitant Medications - SAF
Listing 16.2.9.8.1	Laboratory Results: Hematology - SAF
Listing 16.2.9.8.2	Laboratory Results: Chemistry - SAF
Listing 16.2.9.8.3	Laboratory Results: Urinalysis - SAF

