4.5. SCREEN FAILURES

If the subject does not qualify at Visit 1 or Visit 2, he or she may be re-screened once after 14 days from the relevant visit provided that new informed consent to be signed, new subject number received and all the assessments are repeated as per protocol requirements.

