6. STUDY PROCEDURES

6.1. VISIT DESCRIPTIONS

6.1.1. Visit 1 (Screening): Day minus 14 (± 2 days) prior to Visit 2

The following will be performed/assessed in the order suggested below and all ocular assessments will be conducted in both eyes (as applicable):

- Explain the purpose and conduct of the study to the subject, answer the subject's questions, and obtain written informed consent.
- Obtain information including demographics, concomitant medications, ocular and systemic medical and medication history and surgical history.*
- Assess for prior AT use.
- Evaluate eligibility
- A Screening Identification (ID) should be assigned to the Subject once any Visit 1 procedures (other than Informed Consent Form (ICF)) are performed.
- Subject-rated symptom assessments (in this order):
 - Individual eye dryness and discomfort symptom assessment via VAS
 - SANDE
- Urine Pregnancy Test (UPT) for all eligible women of childbearing potential.*
- Safety Lab Draw (Hematology, Serum Chemistry, Serology and Urinalysis).*
- BCVA
- Slit-lamp biomicroscopy and external eye exam
 - Includes evaluation of conjunctival hyperemia
- CFS (Wait 15 minutes prior to performing Schirmer test)
- Unanesthetized Schirmer test
- IOP
- Dilated Ophthalmoscopy
- Determine if the subject is eligible to continue in the study. Do not continue screening any subject who does not meet eligibility requirements. Any subject who does not meet eligibility requirements will be designated as a Screen Failure.
- If the subject is qualified, a kit containing a two-week supply of Single-Masked Run-In will be provided.
- Subject will self-administer first dose of Single-Masked IP observed by trained study staff.
- Administer the Drop Comfort Tolerability Assessment at 1-minute and 5-minutes post dose.

- Dispense daily dosing diary.
- Instruct the subject to discontinue using all prohibited medications for the remainder of the study and schedule to return to the clinic for Visit 2 in two weeks.

*May be performed at any time during the visit in order to facilitate subject and site schedules.

6.1.2. Visit 2 (Randomization): Day 1

Visit 2 will occur 14 (± 2 days) after Visit 1 (Screening). The following will be performed/assessed in both eyes (as applicable):

- Evaluate continued eligibility
- Subject-rated symptom assessments (in this order):
 - Individual eye dryness and eye discomfort symptom assessment via VAS
 - SANDE
- Use of any concomitant medications since the last visit

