3. SUBJECT POPULATIONS

3.1. Population Definitions

The following subject populations will be evaluated and used for presentation and analysis of the data:

- **Full Analysis Set (FAS)** - includes all randomized subjects who have received at least one dose of the IP. The efficacy and baseline analysis will be performed on the FAS. Subjects in the FAS will be analyzed as randomized.
- **Per Protocol Set (PPS)** - includes subjects in the FAS who do not have protocol deviations that impact the primary efficacy variable, and who complete the study. The PPS will be analyzed using observed data only for efficacy variables. Subjects in the PPS will be analyzed as treated. Sensitivity analyses may be performed on the PPS.
- **Safety Set (SAF)** - includes all randomized subjects who have received at least one dose of the IP. The SAF will be analyzed for all safety assessments. Subjects in the SAF will be analyzed as treated.

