4.8.2. Adverse Events

Adverse events will be coded using the Medical Dictionary for Regulatory Activities (MedDRA) and displayed in tables and listings using System/Organ/Class (SOC) and Preferred Term (PT).

Analyses of adverse events will be performed for those events that are considered treatment emergent, where treatment emergent is defined as any adverse event with onset after the first dose of study medication through the end of the study or any event that was present at baseline but worsened in severity.

Adverse events are summarized by subject incidence rates, therefore, in any tabulation, a subject contributes only once to the count for a given adverse event (SOC or preferred term) by treatment group and overall. In summary tables, SOC will be presented alphabetically and events within SOC will be presented by decreasing frequency count based on the total column.

The frequency and percentage of subjects with any treatment-related ocular and non-ocular TEAE, with any TEAE assessed by the Investigator as related to treatment (definite, probable, or possible relationship), with any TEAE by severity (mild, moderate or severe), and with any serious adverse event (SAE) will be summarized by treatment group and overall. In these tabulations, each subject will contribute only once (i.e., the most related occurrence or the most severe occurrence) to each of the incidence rates in the descriptive analysis, regardless of the frequency of episodes. Furthermore, the frequency and percentage of subjects with any TEAEs by outcome, with any TEAEs by action taken, with any TEAEs by action taken related to study drug will be also summarized in the table by treatment group and overall. Separate summaries will be performed for ocular and non-ocular TEAEs by the most severity and strongest relationship by SOC and PT by treatment group and overall.

Sponsor:	VivaVision Biotech, Inc.		
Protocol:	VVN001-CS-201		
Document Version No.:	V3.0	Document Date:	13-JAN-2022

No formal hypothesis-testing analysis of adverse events incidence rates will be performed.

All adverse events occurring on study will be listed in subject data listings.

By-subject listings also will be provided for the following: subject deaths; serious adverse events; and adverse events leading to withdrawal.

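### The AE, SAE, discontinuation and death listings cover randomized subjects only, so events in subjects dosed with run-in vehicle but never randomized appear in none of them

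*SAP*

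**What the plan says.** SAP 4.8.2 states: "All adverse events occurring on study will be listed in subject data listings". SAP 7.2 names four event listings: 16.2.7.1 "All Adverse Events - SAF", 16.2.7.2 "Serious Adverse Events - SAF", 16.2.7.3 "Adverse Events leading to Discontinuation of Treatment - SAF" and 16.2.7.4 "Subject Deaths - SAF".

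Under SAP 3.1 the Safety Set "includes all randomized subjects who have received at least one dose of the IP. The SAF will be analyzed for all safety assessments". Protocol 9.1.1 also makes randomization a condition of membership.

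Dosing starts before randomization. At Visit 1, Protocol 6.1.1 has the step "Subject will self-administer first dose of Single-Masked IP observed by trained study staff", and run-in vehicle then continues twice daily for about 14 days. Protocol 6.1.2 places an adverse event query at Visit 2 ahead of the decision on eligibility for randomization. Protocol 4.5 foresees failure at Visit 2 and allows one re-screening, with a "new subject number received and all the assessments are repeated as per protocol requirements".

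The only planned outputs on all screened subjects are Table 14.1.1 and Listing 16.2.1.1, both on disposition.

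**The concern.** The run-in is one of the two periods of the study (SAP 2.1), and its product is handled as investigational product. A subject who takes it, has an adverse event and is then not randomized has been exposed on study, and the event is collected. Yet each listing that could show the event's term, dates, severity, seriousness and causality is restricted to a set that this subject cannot enter.

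What is at stake is the completeness of the safety section of the study report. SAP 1.2.1 makes safety and tolerability the primary objective, and Protocol 4.7.1 describes the vehicle as the active drop without VVN001. A serious event or death during run-in in a subject who is not randomized would have no planned listing to appear in. SAP 1.1 makes the SAP's outputs the basis for the report's results sections, so a report that followed the plan exactly would omit it.

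**Working it through.** The plan gives no figure on this point to reproduce, so the check is to follow each type of subject through the text.

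1. **Dosing.** Everyone who qualifies at Visit 1 takes the vehicle before randomization (Protocol 3.1, 4.7.2, 6.1.1).
2. **Leaving after dosing.** Eligibility is tested again at Visit 2 (Protocol 4.3), run-in compliance below 80% excludes (Protocol 4.2, criterion 15), and subjects may stop for other reasons (Protocol 5.1).
3. **Collection.** Adverse events are queried at Visit 2 (Protocol 6.1.2) and recorded in the eCRF for the whole study (Protocol 8.1.2). The data should therefore exist.
4. **Safety Set membership.** Two conditions apply: randomization and a dose of IP. If run-in vehicle counts as IP, a non-randomized subject meets the second but not the first. If it does not count, the subject meets neither. The subject is outside on both readings.
5. **Result by type of subject.**

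| Subject | Run-in vehicle taken | In Safety Set | Events in 16.2.7.1 to 16.2.7.4 | In disposition listing |
|---|---|---|---|---|
| Fails Visit 1 | No | No | Not applicable | Yes |
| Randomized and dosed | Yes | Yes | Yes, run-in events included | Yes |
| Dosed in run-in, not randomized | Yes | No | No | Yes |
| Fails Visit 2, re-screened under a new number, randomized | Yes, twice | New number only | First run-in not covered | Yes |

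The last row holds when membership is applied by subject number. The SAP has no rule that links the two numbers.

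6. **Scale, for illustration only.** The planned number randomized is about 165 (SAP 2.2). The share f of run-in-dosed subjects who are not randomized is not stated, so it is assumed. Subjects dosed = 165 / (1 − f), rounded up; subjects outside the event listings = that number − 165.

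- f = 10%: 165 / 0.9 = 183.3, so 184 dosed and 19 outside
- f = 20%: 165 / 0.8 = 206.3, so 207 dosed and 42 outside
- f = 30%: 165 / 0.7 = 235.7, so 236 dosed and 71 outside
- f = 40%: 165 / 0.6 = 275 dosed and 110 outside

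These are counts of exposed subjects, not of events. The documents give no basis for an event count.

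**The case against.** **The sentence in SAP 4.8.2 can be read more narrowly.** Section 4.8 opens by placing all safety analyses on the Safety Set, and 4.8.2 first confines the AE analyses to treatment-emergent events. The statement that all adverse events are listed may then mean all events as against treatment-emergent ones, within the Safety Set. On that reading Listing 16.2.7.1 does what it promises. This is a fair reading, so the wording is not a flat contradiction. The gap remains on either reading, because no other listing carries these events. SAP 4.2.1 adds a general statement that all study data are listed, but by treatment group, which non-randomized subjects do not have.

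**A reader might infer that these subjects vanish from the report, or that their safety goes unwatched.** The documents do not support that. They are in the all-screened disposition listing, which may show an adverse event or death as the reason for leaving (SAP 4.4), though not the event record. Serious events go to the sponsor within 24 hours (Protocol 8.1.3) whatever a listing's population. The gap is one of display.

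**A reader might also infer that vehicle-intolerant subjects are selectively removed and that the listings hide this.** No criterion excludes a subject merely for having an adverse event in run-in. The specific tests repeated at Visit 2 concern eye dryness, inferior staining, Schirmer score and compliance. Intolerance could act through compliance, hypersensitivity or the investigator's discretion, but nothing shows that it drives failures. Some subjects may simply no longer meet the sign or symptom thresholds.

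**Basing safety tables on the Safety Set is conventional.** That is correct for the by-arm TEAE tables, which need no change.

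**Conclusion.** The point holds as a gap in planned safety reporting. With the listings as titled, adverse events, serious events and deaths in subjects dosed with run-in vehicle but not randomized appear in no event listing. Events from a first run-in under a superseded subject number are exposed to the same gap. This follows from the listing titles and the Safety Set definition, and needs no assumption about rates or about what counts as IP. The re-screening part assumes that the listings are built by subject number.

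The size is unknown. The range of 19 to 110 subjects rests wholly on an assumed 10% to 40% loss after run-in dosing. It should not be turned into a share of vehicle exposure: early stoppers take fewer than 14 days, and a fair denominator would include the randomized subjects' own run-in days (about 165 × 14 = 2,310) as well as the vehicle arm's treatment days (55 × 84 = 4,620).

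No by-arm TEAE table, treatment comparison or efficacy result is affected. The change is still worth making, because it is nearly free and completes the record of events in exposed subjects.

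**What to change.** In SAP 7.2, base Listings 16.2.7.1, 16.2.7.2, 16.2.7.3 and 16.2.7.4 on all subjects who took at least one dose of run-in vehicle or double-masked product. Include 16.2.7.3, since a subject who stops run-in because of an event would otherwise still be missing from it. Add to each listing:

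- a period flag (run-in or double-masked);
- a randomized flag (yes or no), with a not-randomized category where listings are sorted by treatment group;
- a cross-reference to any earlier subject number.

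State the same population in SAP 4.8.2, so that its sentence on listing adverse events has one meaning. Leave the Safety Set definition and the by-arm TEAE tables as they are. A separate summary table for run-in-only subjects is optional once the listings are complete.

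The cost is a few lines of SAP text, four listing titles and a small amount of programming. No new data collection is needed, since the protocol already requires these events to be recorded.
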